### 5.3. Method for Assigning Participants to Treatment Groups

Participants will be randomly assigned to one of two treatment conditions: Bupropion 300 mg/day (n = 180) or placebo (n = 180). We will use small-block randomization by site (Penn or MATER) provided by [name], the study biostatistician. A PHQ-9 score of 10 or greater will be used to identify major depression and stratify the randomization on it. Study site (Penn or MATER) will be the second of the two stratification variables. Study staff and the Investigational Drug Service (IDS) staff will be responsible for medication randomization. The process for randomization is: 1) The research coordinator will complete a “randomization form,” which includes the variables to be entered into the randomization program and fax or email the form without protected health information to the UPenn site; 2) A designated study staff member

Table 1: Medication Dispensing Schedule

	Medication Dispensed For	Morning Dose	Evening Dose	Total Daily Dose
Visit A: Screening	N/A	No medication	No medication	
Visit B: Baseline	Wk 1	150 mg	No medication (for first 3 days); then 150 mg	150 mg
Visit C: Wk 1	Wk 2 through Wk 5	150 mg	150 mg	300 mg
Visit D: Wk 3	N/A	N/A	N/A	N/A
Visit E: Wk 5	Wk 6 through Wk 10	150 mg	150 mg	300 mg
Visit F: Wk 7		150 mg	150 mg	300 mg
Visit G: Wk 10	Endpoint	No medication	No medication	N/A

CONFIDENTIAL

This material is the property of the University of Pennsylvania. Do not disclose or use except as authorized in writing by the study sponsor

Visit H: Wk 24 Post-TQD	N/A	No medication	No medication	N/A
Visit I: 2 wk postpartum	N/A	No medication	No medication	N/A
Visit J: 6 wk postpartum	N/A	No medication	No medication	N/A

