## 7. Statistical Plan

### 7.1. Power

A power analysis is provided only for the primary aims because the exploratory aim is hypothesis generating. Most of our power calculations were approximated as 2-sided t- or z-tests, with  $\alpha = 0.05$ , using PASS Software (Power and Sample Size, NCSS Software, Kaysville, UT). Equivalence testing was approximated as two one-sided tests, with  $\alpha = 0.025$  each.

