#### 7.1.1. Aim 1:

The primary efficacy analysis (**H1**) is a comparison in week 10 (of treatment) and week 24 post-TQD of CO-confirmed 7-day point prevalence quit rates for the placebo and bupropion groups. For the week-10 comparison, we expect that the quit rates in the placebo and bupropion arms would approximate those reported in bupropion trials in the general population of smokers (i.e., placebo = 21.2%; bupropion = 35.9%, OR = 2.1; ref. 44). A sample of 360 provides 88% power to detect a significant between-group effect. The OR for bupropion treatment is similar at 24 weeks, based on Jorenby et al. (168) and our own data, and results from 10 and 24 weeks are highly correlated ( $\rho > 0.7$ ). Thus, we have 80% power to detect a significant difference between treatment arms.

Safety analyses (**H2**) will examine maternal safety across the 10-week treatment and 24-week follow-up periods and fetal and birth outcomes. Key maternal and fetal outcomes to be compared across treatment groups include rates of moderate-to-severe side AEs of bupropion (from the AE checklist). Key birth outcomes will include Apgar scores, birth weight, duration of pregnancy, rate of obstetrical complications, and need for NICU admission. These analyses will involve a test of equivalence because we cannot use standard statistical tests to conclude that a non-significant comparison shows that the drug is safe (i.e., "the absence of evidence is not evidence of its absence"). In our past study with bupropion, 45% of bupropion-treated participants reported no moderate-to-severe AEs, vs. 47% of participants on placebo, a 2% difference. With the present sample size, we will have 82% power to detect similar equivalence between treatment arms on the frequency of moderate-to-severe AEs over the course of the trial, given that AEs are not significantly different between treatment arms, using an equivalence window of 0.30 to 0.60. Likewise, Oncken et al. (47) reported 38% AEs for the placebo group

CONFIDENTIAL

and 25% in the nicotine group. An equivalence test with placebo and bupropion groups both at 30% and an equivalence window for bupropion of +/-15% provides 81% power.

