## **7.2. Statistical Analyses**

[name] will oversee analyses, which will be conducted using Stata, SAS, or R-Language software. Preliminary analyses will assess sample characteristics (e.g., dependence, race) by treatment using t-test or contingency table methods. These variables will also be examined for their relationship to completion of outcome assessments. Variables related to treatment arm or completion of follow ups will be included as covariates in analyses of study aims. Compliance measures will be evaluated across treatment arms, and controlled for in primary analyses. We will examine the correlation between self-report and pill count data and week-5 bupropion plasma levels. We will use intent-to-treat as the primary method to evaluate study aims.

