### **7.2.1. Missing Data:**

We will examine whether the rate of missing data, primarily our smoking cessation outcome data, is related to a range of potential variables, including treatment arm allocation, and demographic and smoking-related variables. Standard bivariate statistical methods will be used to identify correlates of missing data. Variables associated with the rate of missing data ( $p < 0.05$ ) will be included as covariates in the analyses of aims. Items missing at random from assessments will be imputed prior to calculating final scores using conditional means, estimated with an iterated version of Buck's method (173). We will aim to avoid dropout and missed sessions by keeping participants connected to the trial and motivated to complete measures. In our clinical trials, close monitoring of participants and the use of incentives to offset travel costs have resulted in adherence and retention rates >80% (52). Primary analyses will assume that all participants for whom smoking outcome data are unavailable are smokers (intent-to-treat), which is conventional in smoking cessation research. Because this assumption can attenuate the differences between study groups in quit rates, we will also conduct a "completers-only" analysis, as done previously (174).

CONFIDENTIAL

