**H2:** We will compare treatment arms for equivalence of the frequency of moderate-to-severe AEs (individual and total). The hypothesis test for equivalence is a test of whether the OR is out of the prescribed range for the difference between the treatment arms. Using logistic regression, we will conduct two one-sided tests against predefined upper and lower equivalence boundaries on percent reporting only mild AEs. The test-statistic will be the z-score corresponding to the log of the OR. This provides a more valid test of the potential safety of bupropion for pregnant smokers than a simple comparison of mean responses on a measure of AEs.

**H3:** Mean birth weight will be compared for treatment groups using a two-sample t-test, in the context of multiple linear regression. The regression format allows us to add covariates to adjust for imbalances in participant characteristics between treatment arms. Treatment will be entered as a binary indicator. In a secondary analysis, we will also compare the percentage of participants in each group that delivers an infant of LBW (1500-2500 g) or preterm delivery. These secondary hypotheses will be tested using the z-score corresponding to the OR that will be estimated using logistic regression.

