## **PARTICIPANT SAFETY MONITORING PROTOCOL**

**Monitoring Participant Safety.** For this trial, we will use a method to track, manage, and report adverse events that was used in completed studies (14, 43, 52) and is being used in an ongoing (U01 DA020830) pharmacotherapy trial. First, in terms of personnel, each clinical site will include a study physician, a study psychologist, and a research nurse/qualified medical staff person to handle comprehensive eligibility screening, monitoring of participant reactions and adverse events, and the management of any adverse events. The initial eligibility screening procedures will involve careful assessment of participants' medical history to ensure that individuals with pre-existing conditions that can increase adverse event risk are excluded. Second, we will use a two-tiered system to assess potential adverse events. Site staff will complete a baseline adverse event checklist (week 0). At weeks 1, 3, 5, 7, and 10, staff members will conduct an open-ended evaluation of any potential adverse event and complete the established checklist of adverse events. Lastly, as done in our previous clinical trials, participants will be provided with contact information (a wallet-size card) so that, if a serious adverse event occurs, they have methods to contact study staff at their respective clinical site 24 hours a day. Because participants may try to communicate regarding adverse events through the daily text messaging service, which will not be monitored for this purpose, we will provide contact information via an auto-message informing the participant of how to reach study staff in an emergency.

For all adverse events, the site nurse practitioner, in consultation with the site PI and the obstetrician at each site (as needed), will determine a course of action (i.e., continuation and monitoring, dose reduction, participant withdrawal). All adverse events that are considered Serious Adverse Events (see below) will be reported to site PIs and IRBs at all clinical sites, as well as to the FDA and NIH (see below for protocol for adverse event reporting). Site PIs and study physicians will determine whether a serious adverse event requires additional care. Such events may be referred to the outpatient department at the clinical site or to the emergency department of the clinical site (all sites have access to 24-hour emergency services, including extensive inpatient and outpatient services for psychiatric conditions).

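### The H2 equivalence test compares crude proportions of women with a moderate-to-severe AE, with no allowance for women lost before week 10 and no rule for partial or absent AE data

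*Combined protocol and SAP*

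**What the plan says.** Section 7.2.2 (H2) specifies the test: "Using logistic regression, we will conduct two one-sided tests against predefined upper and lower equivalence boundaries on percent reporting only mild AEs". Section 7.1.1 plans it on the "frequency of moderate-to-severe AEs over the course of the trial", using the share of women with no such event: 45% on bupropion and 47% on placebo in an earlier study, with a window of 0.30 to 0.60. A second scenario has 30% with AEs in both arms and a window of ±15 points.

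The systematic assessments are in section 10.1 (Participant Safety Monitoring Protocol): "At weeks 1, 3, 5, 7, and 10, staff members will conduct an open-ended evaluation of any potential adverse event", together with a checklist.

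On the analysis set, section 7.2 says "We will use intent-to-treat as the primary method to evaluate study aims", while section 7.3 limits analysis to women who complied with the protocol.

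On missing data, section 7.2.1 gives a status rule for smoking only (missing counts as smoking). It also offers item-level imputation and covariates related to missingness. Its only retention figure is that methods used in the team's earlier trials "have resulted in adherence and retention rates >80"%. Nothing says whether a woman with one or two AE assessments, or none, is scored AE-free, set to missing or excluded in H2.

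**The concern.** A woman last seen at week 3 has had less opportunity to report an AE than one followed to week 10, yet a logistic model on a per-woman binary treats them alike. The plan's silence can be filled in three ways, and each has a difficulty:

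- **Keep everyone, as intent-to-treat suggests.** Unobserved weeks then count as weeks without an AE.
- **Drop only women with no AE data.** Women lost after week 1, 3, 5 or 7 stay in and are still judged on a 10-week outcome.
- **Restrict to compliant women (7.3).** This may remove women withdrawn under 4.4.1 for drug-related serious AEs or severe psychological symptoms, which is informative for a safety endpoint.

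In a superiority test, shrinking a difference costs power. In an equivalence test it can produce the claim. Section 7.1.1 chose equivalence testing so that absence of evidence would not be read as evidence of safety, and crude proportions under incomplete follow-up weaken that protection. AE frequency is listed among the primary endpoints in section 3.2.

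**Working it through.** **Inputs.** 180 per arm (5.3); two one-sided tests at 0.025 each (7.1); rates and windows from 7.1.1; assessments at weeks 1, 3, 5, 7 and 10. Dropout rates, their timing and a constant AE hazard are assumptions.

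**The plan's own power figures.** Power = Φ((U − d)/SE − 1.96) − Φ((L − d)/SE + 1.96).

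- 45% v 47% AE-free, window 0.30–0.60: d = −0.02, limits −0.17 and +0.13, SE = √[(0.45×0.55 + 0.47×0.53)/180] = 0.0525. Power = Φ(0.896) − Φ(−0.896) = 63%, against a stated 82%.
- 30% v 30%, ±0.15: SE = 0.0483, power 75%, against a stated 81%.

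The stated figures are not reproduced. That is a separate matter, and nothing below depends on it.

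**Effect of permanent loss.** Put the true excess at the margin, where the chance of declaring equivalence should be 2.5%. The window's centre, 45% AE-free, is 55% with an AE; its lower edge, 30% AE-free, is 70%. The 55% is the plan's bupropion rate, used here as the reference rate; the placebo rate is 53%, so 53% v 68% is also run.

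With constant hazard, the probability of a first AE by week t is F(t) = 1 − (1 − p)^(t/10). For a lost woman, the last completed assessment is equally likely to be none, week 1, 3, 5 or 7:

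- p = 0.55: F = 0, 0.077, 0.213, 0.329, 0.428; mean 0.2094.
- p = 0.70: F = 0, 0.113, 0.303, 0.452, 0.569; mean 0.2877.

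With a fraction ℓ lost, the observed rate is (1 − ℓ)p + ℓ × mean. At 20% lost in each arm:

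- Placebo: 0.8×0.55 + 0.2×0.2094 = 0.482.
- Bupropion: 0.8×0.70 + 0.2×0.2877 = 0.618.
- Both rates are about 12% too low in relative terms. The difference is 0.136 instead of 0.150, and SE = √[(0.482×0.518 + 0.618×0.382)/180] = 0.0520.
- P(declare equivalence) ≈ Φ((0.15 − 0.1356)/0.0520 − 1.96) = 4.6%.

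If never-assessed women are excluded (a fifth of those lost, leaving 172.8 per arm), the rates are 0.502 and 0.643, the difference 0.141, SE 0.0527, and the result 3.6%.

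False-equivalence rate, all women counted / never-assessed excluded (nominal 2.5%):

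| True rate, placebo v bupropion | Lost 20% / 20% | Lost 15% placebo / 25% bupropion | Lost 25% placebo / 15% bupropion |
|---|---|---|---|
| 55% v 70% | 4.6% / 3.6% | 16.5% / 9.9% | 0.8% / 1.0% |
| 53% v 68% | 4.7% / 3.7% | 16.2% / 9.8% | 0.9% / 1.1% |
| 30% v 45% | 5.5% / 4.3% | 13.4% / 8.7% | 1.9% / 1.9% |

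At 10% lost in each arm the same model gives about 3.0–3.8%.

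The plan's test statistic is the log odds ratio. For 55% v 70% with 20% lost in each arm and all counted, the limit is ln(0.70/0.30) − ln(0.55/0.45) = 0.647, the observed log OR is 0.551 and its SE 0.214. The rate is Φ((0.647 − 0.551)/0.214 − 1.96) ≈ 6.5%, against 4.6% on the difference scale.

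**Dependence on the unstated rule.** If all of the 20% lost had no assessment and were counted AE-free, the rate would be 8.2% (53% v 68%) to 9.1% (30% v 45%). If they were excluded and missing at random it would stay at 2.5%, with about 144 per arm.

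**The case against.** A reader might infer that the plan scores unassessed women as AE-free and that the test is therefore always pushed toward equivalence. The documents do not support that:

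- **No section states such a rule.** Read literally, a woman with no report is not among those reporting only mild AEs. She could be missing from the logistic model or excluded under 7.3.
- **The five checklist contacts are not the only source.** Section 3.2 adds open-ended questions, obstetric visits and complication-triggered assessments. Section 8.2 requires AE questioning at each contact, 6.11 substitutes telephone assessment, and 6.12 records events since the last visit. Section 10.1 adds prenatal-record abstraction at delivery, though that is directed at obstetric events.
- **Stopping treatment is not loss to assessment.** Sections 5.3, 6.11 and 4.4.2 provide for continued data collection.
- **The direction is conditional.** With heavier placebo loss the test becomes conservative. With no true difference there is no false equivalence to declare.
- **Some handling of missingness exists.** Section 7.2.1 examines it by arm and adds its correlates as covariates.

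Most of this stands. Later contacts can recover an intermittently missed interval, and 20% loss is the worst value compatible with the cited retention. What remains is permanent loss: look-back works only for women who are reached again. Adding covariates to a crude binary does not restore the weeks that were never observed.

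**Conclusion.** The concern holds in a conditional form. H2 is a crude proportion with no allowance for permanent loss before week 10, no classification rule for partial or absent AE data, and conflicting statements on the analysis set. Excluding never-assessed women reduces the distortion but does not remove it, because partly followed women remain.

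With a true excess at the margin, equal loss of 20% gives a modest inflation, to about 3.6–5.5% on the risk-difference scale. A 10-point imbalance toward bupropion gives about 9–17%; the reverse imbalance gives about 1–2%. These figures rest on assumed dropout, constant hazard, uniform timing of loss and no recovery of AEs after the last assessment. The plan supplies no dropout rate for this trial. The supportable conclusion is that the error rate of the safety claim depends on dropout that the analysis does not address, not that a false safety claim is likely.

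**What to change.** In 7.2.2, define the H2 outcome as the week-10 cumulative incidence of a first moderate-to-severe AE. Estimate it by arm with Kaplan-Meier or a discrete-time model, censoring at the last AE contact and counting look-back reports. Apply the equivalence limits to it; the windows in 7.1.1 are already expressed as proportions. At minimum, prespecify this analysis beside the logistic model.

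- State the H2 analysis set as all randomised women who took study drug, and reconcile 7.2 with 7.3.
- State how women with partial or absent AE data are handled in the logistic model, if it is kept.
- Report completed AE assessments by arm.
- Censoring assumes that loss is unrelated to AEs, which may fail. Add a sensitivity analysis that counts women lost on bupropion as having had an AE, or a tipping-point version.

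The cost is SAP wording and some extra analysis of assessments already scheduled, a slightly wider interval and somewhat lower equivalence power.

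### H2 rests the safety conclusion on a joint two-sided equivalence test, so clearly fewer adverse events counts as failure, and the test has about 63-68% and 75-77% power, not the stated 82% and 81%

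*Combined protocol and SAP*

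**What the plan says.** Section 7.2.2 (H2) tests moderate-to-severe AEs by logistic regression: "we will conduct two one-sided tests against predefined upper and lower equivalence boundaries on percent reporting only mild AEs". The statistic is the z-score of the log odds ratio (OR). No numeric OR boundary is given there. Section 7.1 sets the error rate: "Equivalence testing was approximated as two one-sided tests, with $\alpha = 0.025$ each".

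The only windows stand in the power section, 7.1.1, which has two worked examples:
- From a past bupropion study, "45% of bupropion-treated participants reported no moderate-to-severe AEs, vs. 47% of participants on placebo, a 2% difference". For this case, "we will have 82% power to detect similar equivalence between treatment arms", "using an equivalence window of 0.30 to 0.60".
- A nicotine gum trial "reported 38% AEs for the placebo group" "and 25% in the nicotine group". The plan then takes 30% in both arms with a window of 15 points either way, and states 81% power.

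The reason given in 7.1.1 for an equivalence test is that a non-significant difference does not demonstrate safety. H2 in section 2 is worded without direction, as no significant difference between arms. Section 3.2 lists the frequency of moderate or severe side effects among the primary endpoints.

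**The concern.** The safety question has one direction: are moderate-to-severe AEs not much more frequent on bupropion than on placebo? The argument in 7.1.1 justifies testing against a margin. It does not explain why fewer AEs should count against the drug, and no section gives the benefit-side boundary a purpose. Because the joint result is the declared conclusion, a favourable finding in pregnant women could be reported as equivalence not shown. Falling back on the harm side after unblinding would be post hoc. The second boundary also lowers the chance of a positive safety conclusion, and the stated power does not reflect that.

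**Working it through.** **Inputs.** Section 5.3 gives "Bupropion 300 mg/day (n = 180) or placebo (n = 180"), so n = 180 per arm. Section 7.1 gives 0.025 per side, so z = 1.96. Rates and windows are those of 7.1.1. No dropout is stated for H2, and none is applied in steps 1 to 3.

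**Formulas.** L and U are the lower and upper limits, and d is the true effect.
- Power at the lower boundary = Φ((d − L)/se − 1.96); at the upper = Φ((U − d)/se − 1.96); joint power = their sum − 1.
- Risk difference: d = p_b − p_p; se = √[p_b(1−p_b)/180 + p_p(1−p_p)/180].
- Log-OR: d = logit p_b − logit p_p; se = √[1/(180 p_b(1−p_b)) + 1/(180 p_p(1−p_p))].

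**1. The plan's own power figures.**

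Example A: AE-free 45% on bupropion, 47% on placebo; window 0.30 to 0.60; stated power 82%. The lower limit is the harm side.
- Risk difference: d = −0.02, se = 0.0525, limits −0.17 and +0.13. Each side: 0.15/0.0525 − 1.96 = 0.896, giving 81.5%. Joint: 63.0%.
- Log-OR, window referred to 47%: d = −0.0805, se = 0.2115, limits −0.727 and +0.526 (OR 0.48 and 1.69). Harm side 86.4%, benefit side 81.7%, joint 68.1%.
- Log-OR, window referred to 45%: limits −0.647 and +0.606 (OR 0.52 and 1.83). Harm side 76.3%, benefit side 90.1%, joint 66.4%.

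Example B: AE rate 30% in both arms; ±15 points; stated power 81%. On the AE-rate scale the upper limit is the harm side.
- Risk difference: se = 0.0483. Each side: 0.15/0.0483 − 1.96 = 1.145, giving 87.4%. Joint: 74.8%.
- Log-OR: se = 0.230, limits −0.887 and +0.647 (OR 0.41 and 1.91). Harm side 80.3%, benefit side 97.1%, joint 77.4%.

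The joint test therefore gives 63-68% and 75-77%, and neither stated figure is reproduced. Exact binomial enumeration on the log-OR scale (47% reference in A) agrees: 68.7% and 77.3%. Using 0.05 per side does not explain the gap: on the log-OR scale it gives 81.0% for A but 86.5% for B. On the risk-difference scale the joint test would need about 241 and 200 per arm for the stated power.

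**2. Cost of the benefit-side boundary** (harm side alone minus joint).

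| Case | Harm side | Joint | Points lost |
|---|---|---|---|
| A, risk difference | 81.5% | 63.0% | 18.5 |
| A, log-OR, 47% reference | 86.4% | 68.1% | 18.3 |
| A, log-OR, 45% reference | 76.3% | 66.4% | 9.9 |
| B, risk difference | 87.4% | 74.8% | 12.6 |
| B, log-OR | 80.3% | 77.4% | 2.9 |

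**3. A drug with clearly fewer AEs.** Take the gum trial's rates as true here: AE-free 75% on active, 62% on placebo. Risk difference d = +0.13, se = 0.0485; log-OR d = 0.609, se = 0.231.
- Limits ±0.15: benefit side (0.15 − 0.13)/0.0485 − 1.96 = −1.547. Joint 6.1%.
- Limits −0.17 and +0.13: joint 2.5%.
- Log-OR limits from the 0.30 to 0.60 window: joint 1.0% (47% reference) or 2.4% (45% reference).
- Log-OR limits from 30% ±15 points: joint 22.5%, the most lenient reading.
- Harm side alone: over 99.9% in every case.

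If exactly these rates were observed, the 95% confidence interval for the benefit would be 0.13 ± 1.96 × 0.0485, that is +3.5 to +22.5 points. It excludes any increase in AEs, yet crosses the +13 and +15 point limits.

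**The case against.** Much of the case for the plan stands. Each one-sided test runs at the full 0.025, so the harm-side half already is a non-inferiority test with the same limit, error rate and sample size. What is lost is the joint conclusion, not the evidence. Any result that passes both boundaries also passes the harm side, so the benefit-side limit cannot create a false safety claim. The two-sided form matches H2 as worded in section 2. No stopping rule hangs on H2. The 25% and 38% rates come from a nicotine gum trial, whereas the bupropion data cited are slightly worse on drug.

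Four stronger readings are tempting, and the documents do not support them.
- **A uniformly large power loss, say 10 to 30 points.** On the planned log-OR scale, example B loses only 2.9 points. Losses near 28 points need an assumed 20% dropout (144 per arm: example A, risk difference, 72.4% − 44.8% = 27.6), which the H2 power statement does not contain.
- **The upper boundary is the useless one.** That is true only on the AE-free scale. In example B the upper limit is the harm limit.
- **The stated power was computed for a harm-side test.** Single-boundary log-OR values do come close to both figures (81.7% and 80.3%), but in A the match is the benefit side; the harm side there is 86.4%. The documents do not show how the figures arose.
- **The trial could miss harm because of this.** It could not: the harm-side criterion is unchanged.

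**Conclusion.** The point holds and should be fixed, but it is not fatal. The plan makes the joint result the safety conclusion, gives the benefit-side limit no purpose, and states a power that the joint test does not have. At true AE rates of 25% and 38% the joint test passes with about 1-6% probability (23% at most). Under the plan's own rates the extra boundary costs 13-19 points (risk difference) or about 3-18 points (log-OR), and power is overstated by about 4 to 19 points (81 − 77.4 = 3.6; 82 − 63.0 = 19.0). These figures assume 180 evaluable women per arm and the windows of 7.1.1 carried over to the 7.2.2 test; the ranges reflect that the plan fixes neither the reference rate nor numeric OR limits. The error can only withhold a favourable conclusion.

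**What to change.** - **7.2.2 (H2):** prespecify the harm-side test at one-sided 0.025 as the safety conclusion. State the existing harm limit as one numeric OR: 0.30 AE-free is OR (0.30/0.70)/(0.47/0.53) = 0.48 against 47%, or (0.30/0.70)/(0.45/0.55) = 0.52 against 45%. Report the two-sided 95% confidence interval for the OR and for the difference.
- **Section 2 (H2), the Statistical Methodology entry of the Study Summary, and 7.1:** replace the no-difference and equivalence wording with the one-directional statement.
- **7.1.1:** restate power for the harm-side log-OR test: about 86% (47% reference) or 76% (45% reference) for the first example, and 80% for the 30%/30% example. If the two-sided test is kept, state 63-68% and 75-77%.

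This costs text only: no new data, no change in sample size, and no rise in the harm-side error rate. The trial gives up a formal claim of equivalence in both directions. The change should be made before unblinding.
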